4.2.2. Exclusion Criteria

- Patients undergo transplantation of organ(s) in addition to the liver.
- Patients who are enrolled in clinical trials of other unlicensed therapy.
- Patients younger than 18 years
- Patients for retransplant

5. Data Collection Procedure:

Data from January 01, 2010 to December 31, 2025 will be collected from hospital specific database. The collected data will be identified by unique study identifier only. Data will be stored for ten years after study completion in accordance with requirements of the corresponding ethic committees; publication or data source file stored will not contain any personal identifiers.

6. Data Analyses:

All statistical data will be generated by using JMP 13 (SAS Institute, Cary, NC), SPSS 22 statistical package (IBM, Chicago, IL, USA), or R (The R Foundation for Statistical Computing, Vienna, Austria). The main outcome measure will be the incidence of patient survival among different groups. Cumulative overall rejection-free rates will be calculated by Kaplan-Meier methods and differences between curves will be evaluated with the log-rank test and Bonferroni or Holm's correction. Continuous variable data will be analyzed nonparametrically using the Wilcoxon / Kruskal-Wallis' correction.

Categorical variables will be summarized as counts and proportions and compared by Chi squared test or Fisher's exact test as appropriate. These results will be represented as Odd's ratio or Hazard ratio with 95% confidence interval (CI). $P < 0.05$ will be considered statistically significant.

7. Ethical Consideration:

This protocol was approved by the local ethic committees of participating centers. No study activities will begin until approval is obtained. A waiver of informed consent is requested for this study since it meets the requirements for the common rule. Namely, it would be impractical to attempt to obtain consent for this study since many of these patients may now be deceased and/or lost to follow-up. Further, the exclusion of any patients would impact the quality of the study data. Finally, the study involves minimal risk to participants, as no change to patient care is taking place.

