1. SYNOPSIS

Study Title	Elucidating major impact factors for high MELD recipient outcomes after orthotopic liver transplantation in adults.
Trial Design	Retrospective cohort study.
Trial Participants	High MELD patients receiving a liver transplant.
Planned Sample Size and Trial Duration	Eligible patients that received a liver graft within the last 15 years.
Trial duration	Up to 15 years Follow up.
Data Collection Period	January 01, 2010 to December 31, 2025
Primary Objective	To identify main risk factors for long term survival of high Sodium medical Model for End-Stage Liver Disease (NaMELD) patients and long-term graft survival after liver transplantation, with the aim prevent and treat pivotal factors prior to transplantation.
Secondary Objectives	
To confirm the risk factors for other long and short-term complication in high NaMELD patients.
 
To investigate the combination of risk factors and NaMELD graduation over time.

Primary Endpoint	Patient survival after liver transplantation.
Secondary Endpoints	
Assessment of biochemical parameters of liver function in the recipient during the initial postoperative phase and during the Follow up.
 
ICU stay.
 
Reasons for graft loss, death and retransplantation.

2. BACKGROUND AND RATIONALE:

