3. OBJECTIVES

3.1 Primary Objectives

Long-term patient survival of high NaMELD recipients after liver transplantation.

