4.1 Secondary Endpoints

- Biochemical assessment of liver and organ function including laboratory parameters during the Follow up (Day 7, 3 months, 6months, yearly).
- Meaning for health care related parameters including ICU stay.
- Reasons for graft loss, death, and re-transplantation.

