8.2 Recipient Variables

Recipient Variables		
Overall Characteristics	Date of transplant	
	Date of Death	
Biographic Characteristics	Date of Retransplant	
	Date of last clinical visit	
	Age at Transplant	
	Height	
	Weight	
	Gender	
	Etiology of liver Disease	
	Bilirubin; INR; Creatinine; Sodium at MELD	
	Timepoints	
	Creatinine	D1-7
		3 months
		D90
		6months
		yearly
	eGFR	D1-D7
		3 months
		6 months
		yearly
		D90
	INR	6months
		12months
		D7
		3 months
		D90
	AST	6months
		Yearly
		D1 – D7
		3 months
		6months
	ALT	yearly
		D1 – D7
		3 months
		6months
		yearly

	Bilirubin	D7
		3 months
		6months
		yearly
	Sodium	D7
		3 months
		6months
		Yearly
	Alkaline	D7
	phosphatase	3 months
		6months
		Yearly
	Graft Survival at 1, 3, 5, 10 yrs	
Patient Survival at 1, 3, 5, 10 yrs		
Post-transplant ICU Stay		
Readmission within 30 days (1=yes; 0=no)		
Retransplantation date		
Cause of Graft Loss		
Cause of Death		

Freeman, Richard B.; Wiesner, Russell H.; Harper, Ann; McDiarmid, Sue V.; Lake, Jack; Edwards, Erick et al. (2002): The new liver allocation system: moving toward evidence-based transplantation policy. In: Liver Transplantation 8 (9), S. 851–858. DOI: 10.1053/jlts.2002.35927.

Selzner, Markus; Kashfi, Arash; Cattral, Mark S.; Selzner, Nazia; McGilvray, Ian D.; Greig, Paul D. et al. (2010): Live donor liver transplantation in high MELD score recipients. In: Annals of surgery 251 (1), S. 153–157. DOI: 10.1097/SLA.0b013e3181bc9c6a.

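### Section 6 assigns its only Kaplan-Meier/log-rank analysis to rejection-free rates, which are neither a named endpoint nor collected, and assigns patient survival, the primary endpoint, no explicit method that handles censoring

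*Protocol*

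**What the plan says.** The Synopsis gives the primary endpoint as "Patient survival after liver transplantation", and section 3.1 gives the primary objective as "Long-term patient survival of high NaMELD recipients after liver transplantation". Section 4 repeats patient survival as the primary endpoint.

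Section 6 (Data Analyses) opens its outcome description with "The main outcome measure will be the incidence of patient survival among different groups". The next sentence is the only one that names a survival-analysis technique: "Cumulative overall rejection-free rates will be calculated by Kaplan-Meier methods and differences between curves will be evaluated with the log-rank test". The Bonferroni or Holm correction belongs to that same sentence. Section 6 then assigns Wilcoxon/Kruskal-Wallis methods to continuous data and chi-squared or Fisher's exact tests to categorical data. Directly after the categorical tests it adds "These results will be represented as Odd's ratio or Hazard ratio with 95% confidence interval (CI".

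The secondary endpoint nearest to rejection, in section 4.1, is "Reasons for graft loss, death, and re-transplantation". The nearest listed variable, in Appendix 8.2, is "Cause of Graft Loss". Appendix 8.2 also lists the dates of transplant, death, last clinical visit and retransplantation, together with "Patient Survival at 1, 3, 5, 10 yrs" and graft survival at the same four times.

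**The concern.** The outcome given a survival analysis is not the outcome the study is about. Rejection appears once in the protocol, in the Kaplan-Meier sentence. It has no definition, no place among the named endpoints and no dated variable. Patient survival, which carries the primary objective, is called an incidence and is not linked to any method that handles incomplete follow-up.

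Two things are at stake. First, the one stated time-to-event analysis, and the only multiplicity correction in the plan, rest on data that will not be extracted. Second, an analyst who follows the text has no instruction for the primary endpoint. The wording (incidence, and survival at fixed years) leaves room for comparing simple proportions in a cohort where follow-up length depends strongly on the year of transplant.

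**Working it through.** The plan states no figure to reproduce: it gives no sample size, event count or effect size. The check compares passages and adds calendar arithmetic.

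**Step 1. Does rejection have a home in the plan?**

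| Place | Content | Rejection named? |
|---|---|---|
| Synopsis, objectives and endpoints | patient and graft survival, complications in general, biochemistry, ICU stay, reasons for graft loss, death and retransplantation | no |
| Sections 3.1 and 3.2 | long-term patient survival; clinical and laboratory parameters | no |
| Sections 4 and 4.1 | patient survival; biochemistry, ICU stay, reasons for graft loss, death and retransplantation | no |
| Appendix 8.1 (donor) | donor characteristics and laboratory values | no |
| Appendix 8.2 (recipient) | dates, laboratory series, survival, causes of graft loss and death | no event, no date |
| Section 6 | Kaplan-Meier/log-rank sentence | yes, the only mention |

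The cause-of-graft-loss and cause-of-death fields could record rejection as a terminal cause. A rejection-free curve needs the occurrence and date of each first rejection episode, including episodes that did not end in graft loss or death. Those fields cannot supply this.

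**Step 2. What is assigned to patient survival?** Section 6 calls it the main outcome and describes it as an incidence among groups. Neither Kaplan-Meier nor the log-rank test is linked to it. The hazard-ratio sentence follows the categorical tests and names neither a model nor an outcome. A chi-squared or Fisher comparison does not itself produce a hazard ratio, so the sentence does not show which analysis is meant.

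**Step 3. How much censoring does the calendar impose?** Inputs: the data window of January 01, 2010 to December 31, 2025 (Synopsis and section 5) and the survival times of 1, 3, 5 and 10 years (Appendix 8.2).

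- Calendar years in the window: 2025 − 2010 + 1 = 16.
- Latest transplant date that allows *t* full years: December 31 of (2025 − *t*).
- Calendar years of transplant that cannot reach *t* years: *t* of 16.

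| *t* (years) | Latest transplant date with full follow-up | Transplant years without it | Share of window |
|---|---|---|---|
| 1 | Dec 31, 2024 | 2025 | 1/16 = 6.25% |
| 3 | Dec 31, 2022 | 2023–2025 | 3/16 = 18.75% |
| 5 | Dec 31, 2020 | 2021–2025 | 5/16 = 31.25% |
| 10 | Dec 31, 2015 | 2016–2025 | 10/16 = 62.5% |

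These are shares of calendar years, not of patients, because the protocol gives no yearly transplant counts. The Synopsis also speaks of grafts received in the last 15 years. If transplants span 15 calendar years (2011–2025), the last two shares become 5/15 = 33.3% and 10/15 = 66.7%. The conclusion is the same.

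**Step 4. What would a simple proportion do?** Take 10-year survival. For a recipient transplanted in 2016 or later, a death before year 10 can be seen, but survival to year 10 cannot. Three shortcuts are available:

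- Counting everyone not known to be dead as a survivor pushes the proportion up.
- Keeping only patients with known 10-year status retains the recent deaths and drops the recent survivors, which pushes it down.
- Restricting to transplants up to the end of 2015 discards 10 of the 16 calendar years.

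Kaplan-Meier estimation avoids all three, provided censoring is non-informative. Loss to follow-up adds to the administrative censoring; section 7 itself expects some patients to have been lost.

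**The case against.** The strongest reply is that this is a slip of the pen. The preceding sentence names patient survival across groups, the next speaks of differences between curves, and Appendix 8.2 lists the dates that a Kaplan-Meier analysis of survival needs. On that reading, rejection-free is a wrong word in a paragraph about survival. This is plausible, but nothing in the protocol confirms it, and a slip in the sentence that should govern the primary endpoint still has to be corrected.

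A statistical analysis plan may also exist and may specify the survival model. That would answer a complaint about missing detail. Here the protocol states a method and attaches it to an outcome it neither names as an endpoint nor collects, and that sentence would still be wrong.

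Three stronger readings are tempting and should be resisted:

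- A reader might infer that patient survival will be tested by chi-squared, Fisher or Wilcoxon methods. The protocol assigns those tests to categorical and continuous variables generally and never to patient survival.
- A reader might infer that no time-to-event model is intended at all. The promise of a hazard ratio speaks against that, although it is tied to no model or outcome.
- A reader might infer that rejection lies wholly outside the study's aims. The Synopsis has a secondary objective on other long- and short-term complications, which could include rejection. The supportable statement is that rejection is not named as an objective or endpoint and has no event or date on the data list.

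It is also fair to say that the study is retrospective and that no patient's care or data capture for survival depends on this sentence. That makes the correction easy but does not remove the need for it.

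**Conclusion.** The point holds as a misstatement about the primary endpoint's analysis. The single Kaplan-Meier/log-rank analysis and its multiplicity correction are assigned to an outcome that cannot be computed from the listed variables. Patient survival has no explicitly assigned method that handles censoring.

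The size that can be shown is the censoring built into the calendar: no complete 10-year follow-up for transplants in 10 of 16 calendar years, and no complete 5-year follow-up in 5 of 16. This assumes that transplants are included throughout the data window and that follow-up stops at its end. The size of any bias in a group comparison cannot be calculated, because the protocol gives no patient numbers, event rates or distribution of NaMELD groups over time. It would matter most if the groups being compared had different transplant years and so different follow-up.

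The documents do not show that survival will in fact be analysed without regard to censoring, only that the protocol does not say otherwise.

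**What to change.** In section 6:

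- Replace rejection-free rates with patient survival as the Kaplan-Meier/log-rank outcome. Define it as the time from transplant to death from any cause, censored at the last clinical visit or data cut-off.
- Keep the multiplicity correction as stated and attach it to these comparisons. Choosing between Bonferroni and Holm is not needed to repair this error.
- Tie the hazard ratio to a named time-to-event model for patient survival, for example Cox regression, and separate that sentence from the categorical tests.
- If graft survival, which the Synopsis includes in its primary objective, is analysed in the same way, define its event, stating how graft loss, retransplantation and death each count.
- Delete rejection-free rates. If rejection is truly of interest, list it as a secondary endpoint and add its date to Appendix 8.2.

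For patient survival the cost is a sentence or two of text. The dates of transplant, death and last clinical visit are already on the data list. Only the option of keeping rejection would require extra data extraction.

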2.1 Liver Transplantation and Model for End-Stage Liver Disease

Liver transplantation (LT) represents an important curative option for end stage liver disease such as decompensated cirrhosis, which remains a major challenge for today's health care system. The Model for End-Stage Liver Disease (MELD) is a worldwide-established scoring system for the evaluation of the severity of liver disease in allocation processes. However, the interpretation of MELD in clinical practice, particularly with regard to prioritizing potential liver transplant recipients, has revealed some hazards. These include the adaptation of MELD based on patient's characteristics, e.g. the presence of hepatocellular carcinoma, kidney failure and cardiovascular disease (Freeman et al. 2002). In addition, the remaining paucity of organ donors contributes to a rising number of transplantations of high MELD recipients. This leads to the risk of impaired outcomes, especially considering the interaction of additional donor and recipient risk factors, such as extended cold preservation, kidney function and warm ischemia (Schlegel et al. 2017). For a certain patient cohort living donation might represent a feasible approach as reported previously for high MELD patients (Selzner et al. 2010). Overall, the interaction of donor and recipient characteristics on the outcomes after LT in high MELD patients remains a scarcely investigated field. Therefore, the identification of factors influencing patient's outcomes after orthotopic liver transplantation becomes increasingly important, especially in high MELD recipients.

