2.2 Aim of the Study

We will create a comprehensive database to address several questions regarding the selection and outcome of liver transplantation in high NaMeld recipients:

1. Is the change of NaMeld score (delta Meld) prior to liver transplantation predictive for post-transplant outcome?
2. What are the characteristics of futile liver transplants in high NaMeld patients (high NaMeld recipients that do well vs early death)
3. Is exceeding the NaMeld threshold of 30 predictive of poor outcome?
4. Do all NaMeld factors are of equal importance for the prediction of futile outcome in high Meld recipients?

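### The synopsis sets out to find risk factors for survival, but section 6 names only unadjusted one-variable tests and gives its hazard ratios no estimator

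*Protocol*

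**What the plan says.** The synopsis states the primary objective as "To identify main risk factors for long term survival of high Sodium medical Model for End-Stage Liver Disease (NaMELD) patients and long-term graft survival", with a view to acting on those factors before transplantation. Section 3.1 is narrower: "Long-term patient survival of high NaMELD recipients after liver transplantation". The primary endpoint is patient survival in both the synopsis and section 4.

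Two further questions concern factors jointly. A secondary objective in the synopsis is "To investigate the combination of risk factors and NaMELD graduation over time". Aim 4 in section 2.2 asks "Do all NaMeld factors are of equal importance for the prediction of futile outcome in high Meld recipients".

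Section 6 names these methods:
- Kaplan-Meier curves of rejection-free rates, compared by log-rank with a Bonferroni or Holm correction.
- Wilcoxon/Kruskal-Wallis for continuous variables.
- For the rest: "Categorical variables will be summarized as counts and proportions and compared by Chi squared test or Fisher's exact test as appropriate".

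The next sentence reads "These results will be represented as Odd's ratio or Hazard ratio with 95% confidence interval (CI", and significance is set at P < 0.05. Section 6 names no Cox, logistic or other regression model.

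**The concern.** Finding which factors matter most, or whether the parts of one score carry equal weight, means estimating each factor's association with survival while the others are held fixed. None of the tests in section 6, as stated, does this. A factor that merely accompanies a real risk factor will look like one. Because the synopsis wants to prevent and treat the factors found, a mistaken factor could be taken up as a target.

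There are two further problems. Read literally, the time-to-event methods serve rejection and not the primary endpoint, which leaves patient survival to tests that ignore censoring. And the reader is promised hazard ratios without being told what will estimate them.

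**Working it through.** The protocol states no sample size, power or event count, so there is no figure to reproduce. The check sets the text side by side and then illustrates the size on assumed inputs.

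**1. Questions against methods.**
- Risk factors for patient survival (synopsis): needs an adjusted time-to-event model. Section 6 names none.
- Relative weight of bilirubin, INR, creatinine and sodium (aim 4; Appendix 8.2 lists them together, at the MELD time points): needs all four in one model. Section 6 sends continuous variables to Wilcoxon/Kruskal-Wallis, one at a time and without using time to death.
- Patient survival curves: section 6 calls patient survival the main outcome measure, but attaches Kaplan-Meier and log-rank to rejection-free rates. Rejection is neither an endpoint in section 4 nor a variable in Appendix 8.

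**2. Where a hazard ratio could come from.** A 2x2 table gives an odds ratio directly. Chi-squared, Fisher, Wilcoxon and Kruskal-Wallis give no hazard ratio. The log-rank test can: in 500 simulated data sets with a true HR of 1.5, the median was 1.50 from the Peto one-step estimate, 1.50 from observed/expected counts and 1.50 from a one-variable Cox model. That estimate is unadjusted, and section 6 names it neither as the estimator nor for patient survival.

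**3. Unequal follow-up.** The data window runs from 1 January 2010 to 31 December 2025, which is 16 calendar years. Assume even accrual and follow-up to the end of the window.
- Ten full years are possible only for transplants in 2010 to 2015: 6/16 = 37.5%.
- Five full years are possible for transplants in 2010 to 2020: 11/16 = 69%.

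A contingency or rank test of dead against alive treats all these patients as equally observed.

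**4. Confounding, by hand (assumed inputs).** Let factor X have no effect, and let a real risk factor Z with hazard ratio h be present in a proportion p1 of patients with X and p0 of those without. At the start of follow-up the apparent hazard ratio for X is (p1·h + 1 − p1)/(p0·h + 1 − p0).
- p1 = 0.40, p0 = 0.20, h = 1.5: 1.2/1.1 = 1.09
- p1 = 0.40, p0 = 0.20, h = 2: 1.4/1.2 = 1.17
- p1 = 0.65, p0 = 0.35, h = 2: 1.65/1.35 = 1.22

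**5. Confounding, by simulation (assumed inputs).** The third case was run 500 times with 500 patients, a baseline hazard of 0.05 per year, censoring uniform over 0 to 15 years, both factors at 50% prevalence and a correlation of 0.3. The median number of deaths was 194.
- Unadjusted: median HR for X 1.24, close to the hand figure; log-rank significant in 30% of runs.
- Cox model with X and Z: median HR for X 1.01; significant in 6% of runs.

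**6. Number of candidates.** Appendix 8.1 gives 7 donor characteristics and 4 or 5 laboratory values (depending on whether AST/ALT counts as one or two), so 11 or 12. Appendix 8.2 gives 5 recipient characteristics and the 4 score components, so 9. The total is 20 or 21. With every candidate null, tests independent and no correction, the chance of at least one false factor is 1 − 0.95^20 = 0.64 to 1 − 0.95^21 = 0.66. With Bonferroni at 0.05/20 = 0.0025 it is 1 − 0.9975^20 = 0.049.

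**The case against.** Several parts of the opposing case stand.

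- **Interaction.** A reader might infer that the primary objective includes donor-recipient interaction, because section 2.1 says "the interaction of donor and recipient characteristics on the outcomes after LT in high MELD patients remains a scarcely investigated field". That is background. Neither statement of the primary objective mentions interaction, so the absence of an interaction test is not a failure of that objective. Section 2.1 also names no specific donor-by-NaMELD term, and two of its examples, cold preservation and warm ischemia, are not in Appendix 8.
- **Multiplicity.** A reader might infer that all testing runs at an uncorrected 0.05. Section 6 states Bonferroni or Holm for the curve comparisons. It attaches no correction to the other tests, but it does not describe a factor screen either. The 0.64 to 0.66 assumes independence, whereas the confounding argument rests on associated factors. It is a reference figure and not the size of this point.
- **Hazard ratios.** A reader might infer that none of the named tests can yield one. That is too strong, since log-rank quantities give an unadjusted hazard ratio. The sentence promising odds or hazard ratios could also be meant for section 6 as a whole.
- **A separate SAP.** Section 6 does not exclude regression, and covariate lists, model checks and interaction terms are ordinary SAP content. Their absence is not the point here.
- **Assumed inputs.** The protocol gives no data on how its factors are associated, and the milder hand examples give only 1.09 to 1.17.

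What remains is more than silence. Section 6 states a set of methods, and that set does not fit the objective in the synopsis or aim 4. It assigns the survival method to an outcome that is not an endpoint, and it places the hazard ratio directly after tests that cannot produce it.

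**Conclusion.** The point holds as a mismatch between what the protocol sets out to learn and the methods it names. If section 6 is followed as written, the results on risk factors are unadjusted, and the rank and contingency tests also ignore unequal follow-up. Aim 4 cannot be answered by separate tests of the four components.

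The documents do not fix the size. On the assumed inputs, a factor with no effect showed an apparent HR of 1.09 to 1.24, and in the simulated case it was declared significant in 30% of runs against 6% after adjustment. The true distortion depends on associations and death counts that the protocol does not give. The textual mismatch depends on none of these assumptions.

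**What to change.** Change section 6 as follows:
- Apply Kaplan-Meier and log-rank to patient survival.
- Make the primary risk-factor analysis a multivariable Cox model for patient survival, with prespecified pre-transplant donor and recipient covariates from Appendix 8, including donor type and transplant year or era (the date of transplant is collected).
- Enter either the NaMELD score or its components, not both in the same model, because the score is built from them. Use the component model for aim 4.
- Limit the number of terms to what the observed deaths can support.
- Report adjusted hazard ratios with 95% CI, and name the Cox model as their source.
- Keep the one-variable tests as description.
- Treat any interaction terms as exploratory and limit them to variables actually collected.

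The covariate list and model checks may sit in a SAP if section 6 names the model and refers to it. The date of transplant, date of death and date of last visit are already in Appendix 8.2, and all three named software packages fit Cox models. The cost is a few sentences, a little more analysis work, and fewer factors reaching significance.
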